7.3.1 Efficacy parameters

There will be no assessment for efficacy over the course of the study as the subjects are HIV-1 seronegative volunteers.

7.3.1 Safety parameters

All patients who have at least one dose of the trial medication, whether withdrawn prematurely or not, will be included in the safety analysis.

All safety data and adverse events will be summarised.

7.4 Criteria for termination of the trial

The Sponsor or Investigator may terminate either part of, or the entire study for safety or administrative reasons. A written statement fully documenting the reasons for such a termination will be provided to the Ethics Committee and the Regulatory Authority as appropriate.

7.5 Toxicity Management

In the event of a discontinuation of a DTG for suspected drug induced liver injury, other clinically significant liver chemistry elevations, severe skin reaction or hypersensitivity reaction, subjects should not be re-challenged with a DTG-containing product due to the risk of a recurrent reaction. These subjects should be withdrawn from study.

- Allergic reaction**

Subjects with Grade >1 or higher allergic reactions that are considered to be possibly or probably related to the investigational product should permanently discontinue the investigational product and the subject should be withdrawn from the study. Subjects should be treated as clinically appropriate and followed until resolution of the adverse event.

- Rash**

Participants should be instructed to contact the Investigator as soon as possible if they develop a rash while on study. Mild to moderate rash is an expected adverse reaction for DTG-containing antiretroviral therapy.

Subjects should permanently discontinue investigational product (and all other concurrent medication(s) suspected in the Investigators causality assessment) for a rash Grade 1 or higher, and the subject should be withdrawn from the study. Subjects should be treated as clinically appropriate and followed until resolution of the adverse event.

The rash and any associated symptoms should be reported as adverse events and appropriate toxicity ratings will be used to grade the events (based on DAIDS [Division of AIDS] toxicity grading).

- **Liver Chemistry Stopping and Follow up Criteria** Summarized in Appendix 5.

- **Suicidal Risk Monitoring**

Subjects will be monitored appropriately and observed closely for suicidal ideation and behaviour, or any other unusual changes in behaviour. Mental health consultation will be considered or referral for subjects who experience signs of suicidal ideation or behaviour.

Subjects with evidence of suicidal ideation or behaviour changes should permanently discontinue the investigational product and the subject should be withdrawn from the study.

If any subject experiences a possible suicidality-related adverse event (PSRAE) while participating in this study that will be considered to meet ICH E2A (ICH E2A, 1994) definitions for seriousness, we will collect information using a PSRAE case report form in addition to reporting the event on a serious adverse event case report form. A PSRAE may include, but is not limited to, an event that involves suicidal ideation, a preparatory act toward imminent suicidal behaviour, a suicide attempt, or a completed suicide. The investigator will exercise his or her medical and scientific judgment in deciding whether an event is possibly suicide-related. PSRAE forms should be completed and reported to Chelsea and Westminster NHS Trust R&D within one week of the investigator diagnosing a possible suicidality-related serious adverse event.

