8.1 Definitions

An adverse event (AE) is any untoward medical occurrence in a subject administered a pharmaceutical product and which does not necessarily have a causal relationship with the study

treatments. An AE can therefore be any unfavourable and unintended sign (including an abnormal laboratory finding), symptom, or disease temporally associated with the use of a medicinal (investigational) product, whether or not considered related to the medicinal (investigational) product.

Adverse events observed by the investigator, or reported by the subject, and any remedial action taken, will be recorded in the subject's CRF and should be verifiable in the subject's notes throughout the study. The nature of each event, time of onset after drug administration, duration and severity will be documented together with the Investigator's opinion of the causal relationship to the treatment (unrelated, unlikely, possible, probable, and definite).

All subjects experiencing adverse events, whether considered associated with the use of the study medication or not, must be monitored until the symptoms subside and any clinically relevant changes in laboratory values have returned to baseline, or until there is a satisfactory explanation for the changes observed.

Procedures such as surgery should not be reported as adverse events. However, the medical condition for which the procedure was performed should be reported if it meets the definition of an adverse event. For example, an acute appendicitis that begins during the adverse event reporting period should be reported as the adverse event and the resulting appendectomy noted on the CRF.

Planned procedures such as surgery planned prior to the subject's enrolment into the study need not be reported as adverse events if these are documented as planned at the screening visit.

Clinically significant changes in physical examination and blood safety profiles should also be recorded as adverse events.

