8.1.2 Assessment of Causality

The relationship to study drug of each adverse event will be assessed using the following definitions:

DEFINITE: Distinct temporal relationship with drug treatment. Known reaction to agent or chemical group, or predicted by known pharmacology. Event cannot be explained by subject's clinical state or other factors.

PROBABLE: Reasonable temporal relationship with drug treatment. Likely to be known reaction to agent or chemical group, or predicted by known pharmacology. Event cannot easily be explained by subject's clinical state or other factors.

POSSIBLE: Reasonable temporal relationship with drug treatment. Event could be explained by subject's clinical state or other factors.

UNLIKELY: Poor temporal relationship with drug treatment. Event easily explained by subject's clinical state or other factors.

UNRELATED: This is an event which occurs before dosing. Event or intercurrent illness is due wholly to factors other than drug treatment.

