8.2 Collection and follow up of adverse events

All adverse events, however minor, will be documented in the CRF whether or not the investigator concludes the event to be related to drug treatment.

The adverse event reporting period will be from the time that the subject gives informed consent until the subjects final study visit. In addition, any untoward event that may occur subsequent to the reporting period that the Investigator assesses as possibly, probably or definitely related to the study drug medication should also be reported as an adverse event (AE).

Adverse events may be directly observed, reported spontaneously by the subject or by questioning the subject at each study visit.

All AE should be followed up until they are resolved or the subject's participation in the study ends (i.e. until the final CRF is completed for that subject). In addition, all serious and non-serious adverse events assessed by the Investigator as possibly related to the investigational medication should continue to be followed even after the subject's participation in the study is over. Such events should be followed until resolution, or until no further change can reasonably be expected. Deaths occurring more than 30 days after the final dose, which are considered to be unrelated to the study medication, should not be reported as SAE.

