Appendix 4: Risk Assessment: Dolutegravir (TIVICAY)

Potential Risk of Clinical Significance	Data/Rationale for Risk	Mitigation Strategy
Investigational Product: dolutegravir Refer to the most recently approved SmPC for this trial		
Hypersensitivity and rash	Hypersensitivity reactions have been reported with dolutegravir, and were characterized by rash, constitutional findings, and sometimes, organ dysfunction, including severe liver reactions. Further information on this risk is provided in Section 7.5 .	Subjects with history or presence of allergy/sensitivity to any of the study drugs or their components are excluded Specific/detailed toxicity management guidance is provided for hypersensitivity reactions and rash (Section 7.5) The subject informed consent form includes information on this risk and the actions subjects should take in the event of a hypersensitivity reaction or associated signs and symptoms. Subjects will be monitored for symptoms of hypersensitivity reactions and stop treatment immediately should they appear. These symptoms include, but not limited to, severe rash or rash accompanied by raised liver enzymes, fever, general malaise, fatigue, muscle

Potential Risk of Clinical Significance	Data/Rationale for Risk	Mitigation Strategy
Investigational Product: dolutegravir Refer to the most recently approved SmPC for this trial		
		
or joint aches, blisters, oral lesions, conjunctivitis, facial oedema, eosinophilia, angioedema).
 
Clinical status including liver aminotransferases and bilirubin should also be monitored. Delay in stopping treatment with dolutegravir or other suspect active substances after the onset of hypersensitivity may result in a life-threatening allergic reaction.

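### Allergic-reaction stopping rule (Section 7.5): unclear grade threshold, definite causality not named, and narrower than Appendix 4 for non-rash reactions; a small gap that is easy to close

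*Combined protocol and SAP*

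**What the plan says.** The allergic-reaction bullet in Section 7.5 (Toxicity Management) applies to "Subjects with Grade >1 or higher allergic reactions that are considered to be possibly or probably related to the investigational product". Those subjects stop dolutegravir for good and leave the study.

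The rash bullet directly below it orders the same action "for a rash Grade 1 or higher". It sets no causality condition for dolutegravir; causality matters there only for other medicines taken at the same time.

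The opening paragraph of Section 7.5 covers what follows once dolutegravir has been stopped for certain reasons. After "severe skin reaction or hypersensitivity reaction, subjects should not be re-challenged with a DTG-containing product", and they are withdrawn.

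Section 8.1 gives the causality scale: "unrelated, unlikely, possible, probable, and definite". Section 8.1.2 defines the top level separately: "DEFINITE: Distinct temporal relationship with drug treatment". Section 8.2 uses the scale in two ways. Its late-reporting sentence covers events "possibly, probably or definitely related to the study drug medication". A later sentence, on continued follow-up, covers events "assessed by the Investigator as possibly related to the investigational medication should continue to be followed".

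In Appendix 4, the hypersensitivity row says that subjects are "monitored for symptoms of hypersensitivity reactions and stop treatment immediately should they appear". It attaches no grade or causality condition, and it points to Section 7.5 for the detailed guidance.

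**The concern.** This sentence decides when a healthy volunteer stops the study drug, so it should give one answer for a given reaction. As written, a Grade 1 allergic reaction without rash can be read as inside or outside it, and the strongest causality level is not mentioned. Appendix 4 sends the reader to Section 7.5 for detail, and the reader finds conditions there that Appendix 4 does not have.

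Appendix 4 itself warns that late stopping after the onset of hypersensitivity can have life-threatening consequences. Subjects dose themselves at home, and Appendix 1 shows no scheduled visit between Day 1 and Day 28 or between Day 44 and Day 72. Staff may therefore have to apply the rule to an unscheduled report. The subjects are HIV-negative, and Section 7.3.1 states that no efficacy is assessed, so nothing is gained by leaving doubt about when to stop.

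**Working it through.** There is no power, alpha or event-rate figure to reproduce. The check is a comparison of texts, with two small counts.

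**Step 1: grade.** Grade >1 means Grade 2 and above, which makes the words that follow it redundant. The rash rule includes Grade 1. The allergic-reaction bullet mixes the two forms, so nobody can tell whether a different threshold was meant. If the symbol were a misread ≥, Grade 1 would be included and the redundancy would remain. The ≥ sign survives elsewhere in the text (Section 8.3, Appendix 4, Appendix 5), so the text is taken as it stands.

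**Step 2: causality.** The scale has 5 levels, 3 of them possible or stronger. Section 7.5 names 2 of those 3. Section 8.2 names 3 of 3 in one sentence; in another it uses possible alone, evidently as a floor.

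**Step 3: Section 7.5 against Appendix 4, by type of reaction.**

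| Reaction | Section 7.5 bullets, read literally | Appendix 4 |
|---|---|---|
| Rash, Grade 1 or above | Stop and withdraw, whatever the causality | Lists severe rash, or rash with other signs |
| No rash, Grade 2 or above, possible or probable | Stop and withdraw | Stop at once |
| No rash, Grade 2 or above, definite | Not named; a sensible reader would stop | Stop at once |
| No rash, Grade 1, possible or probable | Unclear; the symbol alone excludes it | Stop at once |
| No rash, judged unlikely or unrelated | No action | Stop at once on symptoms |

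The Appendix 4 entries for reactions without rash assume that the reaction counts as a hypersensitivity symptom. Where it does, the opening paragraph of Section 7.5 then rules out re-challenge and leads to withdrawal.

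The first row shows Section 7.5 as the stricter text. The second shows agreement that dosing stops. The third is a wording gap only. The fourth is the main unresolved case. In the fifth, Appendix 4 acts on symptoms, while the Section 7.5 bullet depends on a causality judgement.

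**Step 4: cost of one more withdrawal.** Section 4.1 plans 16 subjects, 8 per group. One withdrawal is 1/16 = 6.25% of the sample and 1/8 = 12.5% of a group. The subject also leaves the evaluable cohort (Section 7.2) unless replaced (Section 4.3). The documents give no allergic-reaction rate, so no expected number can be stated.

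**The case against.** The strongest reply is that this is copy-editing, because other provisions already protect the subject. Appendix 4 requires an immediate stop, any rash of Grade 1 or above ends dosing, and Section 4.3 lets the investigator withdraw a subject for an adverse event. Much of this stands, and it is why the point is minor. It does not remove the point. The opening of Section 7.5 says what follows a discontinuation, not when to discontinue. Section 4.3 gives a discretion and also asks that unnecessary withdrawals be avoided. Appendix 4 is the real safeguard, and it is the text with which the Section 7.5 bullet disagrees.

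A second reply is that naming possible and probable sets a floor, as one sentence of Section 8.2 does. That is very likely what was meant. A reader might infer that a subject with a definite reaction could be kept on dolutegravir. The documents do not support this: the omission looks like a drafting slip, and Appendix 4 would stop such a subject in any case.

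A third reply is that an ungraded immediate stop and a graded rule for permanent discontinuation can coexist, since the actions differ. This has some force. But once dosing has stopped for hypersensitivity, the opening of Section 7.5 makes the stop permanent and adds withdrawal, so the two rules meet in the same outcome.

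Finally, Appendix 4 describes hypersensitivity largely in terms of rash with other signs, and the severity table is only linked in Appendix 3. How it would grade a mild non-rash allergic reaction cannot be read from the documents. This stands as a limit. The symptom list in Appendix 4 is expressly not exhaustive, so such reactions may fall under it, but that is a reading and not a stated fact.

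**Conclusion.** The concern holds as a minor correction to a safety rule. The allergic-reaction bullet in Section 7.5 has an incoherent grade threshold, does not name definite causality and, for non-rash reactions, is narrower than the Appendix 4 instruction that relies on it for detail.

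The practical gap is small: mainly Grade 1 allergic reactions without rash. That rests on two assumptions: that investigators treat a definite reaction at least as seriously as a probable one, and that Appendix 4 is followed as an operative instruction.

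A reader might go further and infer that Section 7.5 is looser than Appendix 4 throughout, or that subjects are left without a stopping rule for hypersensitivity. Neither follows. For rash, Section 7.5 is the stricter text, and Appendix 4 supplies an immediate stop. Sample size, power and the primary analysis are not affected.

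**What to change.** Amend Section 7.5 only. Replace the trigger sentence with wording such as:

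*Any subject with an allergic reaction of Grade 1 or above, judged possibly, probably or definitely related to dolutegravir, stops dosing at once, does not restart, and is withdrawn. Dosing also stops at once when symptoms of hypersensitivity appear, whatever their grade or assessed causality (see Appendix 4).*

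This matches the grade in the rash rule and removes the difference from Appendix 4. Two alternatives should be avoided. A Grade 2 threshold would recreate the conflict, because a stop for hypersensitivity under Appendix 4 already leads to withdrawal through the opening of Section 7.5 at any grade. Adding a threshold to Appendix 4 would weaken an immediate stop.

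The cost is a numbered and dated protocol amendment (Section 11.1) and possibly an occasional extra withdrawal, at the 1-in-16 cost shown above, with replacement available under Section 4.3. Naming the definite level and stating the immediate stop add nothing beyond what Appendix 4 already asks.

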7.6 Avoidance and Management of Pregnancy

Due to the potential risk from neural tube defect associated with DTG treatment during the first trimester of pregnancy, study staff must review the following information with all female participants of reproductive potential:

- Participants should be informed that in an early analysis of one observational study, women who were taking DTG when they became pregnant had an increased risk of having babies with serious brain and spine defects. These defects happen early in pregnancy, before many women even know they are pregnant.
- Women of reproductive potential should be counselled on the importance of avoiding pregnancy, safer sexual practices and the proper use of their chosen contraceptive methods in accordance with the applicable contraceptive product label, or, for non-product methods, as determined by the investigator.

- The need for the participant's chosen contraceptive method to be used for an adequate time period before dosing with the DTG is initiated.
- The need to continue the use of contraception throughout the treatment- and post-treatment- periods with DTG, until it is predicted that a clinically insignificant amount of DTG is present in the participant (i.e. 30 days or one month after stopping DTG).
- Females of reproductive potential should be reminded about the importance of pregnancy avoidance and of adherence to contraception requirements at every study visit.

Additionally, site staff should document the participant's chosen contraception methods in her medical records and study records/eCRF.

Any subject who becomes pregnant during the study should be immediately withdrawn from DTG, to eliminate further exposure to the embryo/foetus, and withdrawn from the study. Any pregnancy that occurs during study participation must be reported using the Pregnancy CRF (Appendix 6). To ensure subject safety, each pregnancy must be reported to the PI and the nominated person at the sponsor Chelsea and Westminster NHS Trust research and development (R&D) office (as set by the sponsor standard operating procedures (SOP)), within 24 hours of learning of its occurrence. The pregnancy should also be reported to ViiV Healthcare in accordance with the terms of the contract. The pregnancy must be followed up to determine outcome (including premature termination) and status of mother and child, which must also be reported to the PI and the nominated person at the sponsor R&D office, using a the Pregnancy Follow-up CRF (Appendix 6). The pregnancy outcome should also be reported to ViiV Healthcare within one week of awareness in accordance with the contract. Pregnancy complications and elective terminations for medical reasons must be reported as an adverse event or serious adverse event. Spontaneous abortions must be reported as a serious adverse event.

Any serious adverse event occurring in association with a pregnancy brought to the investigator's attention after the subject has completed the study and considered by the investigator as possibly related to DTG, must be promptly reported to the PI and the nominated person at the sponsor R&D office and ViiV Healthcare.

8 Adverse Events

8.1 Definitions

An adverse event (AE) is any untoward medical occurrence in a subject administered a pharmaceutical product and which does not necessarily have a causal relationship with the study

treatments. An AE can therefore be any unfavourable and unintended sign (including an abnormal laboratory finding), symptom, or disease temporally associated with the use of a medicinal (investigational) product, whether or not considered related to the medicinal (investigational) product.

Adverse events observed by the investigator, or reported by the subject, and any remedial action taken, will be recorded in the subject's CRF and should be verifiable in the subject's notes throughout the study. The nature of each event, time of onset after drug administration, duration and severity will be documented together with the Investigator's opinion of the causal relationship to the treatment (unrelated, unlikely, possible, probable, and definite).

All subjects experiencing adverse events, whether considered associated with the use of the study medication or not, must be monitored until the symptoms subside and any clinically relevant changes in laboratory values have returned to baseline, or until there is a satisfactory explanation for the changes observed.

Procedures such as surgery should not be reported as adverse events. However, the medical condition for which the procedure was performed should be reported if it meets the definition of an adverse event. For example, an acute appendicitis that begins during the adverse event reporting period should be reported as the adverse event and the resulting appendectomy noted on the CRF.

Planned procedures such as surgery planned prior to the subject's enrolment into the study need not be reported as adverse events if these are documented as planned at the screening visit.

Clinically significant changes in physical examination and blood safety profiles should also be recorded as adverse events.

8.1.1 Assessment of severity

Severity should be recorded and graded according to the current version of the Division of AIDS (DAIDS) Table for Grading the Severity of Adult and Paediatric Adverse Events (Appendix 3).

Note: There is a distinction between the gravity and the intensity of an adverse event. Severe is a measure of intensity; thus, a severe reaction is not necessarily a serious adverse event. For example, a headache may be severe in intensity but would not be classified as serious unless it met one of the criteria for serious events.

